5.3.2 Eligibility Criteria/Vulnerable Populations

Adult inpatients within the Yale New Haven Health System who meet the following criteria:

Inclusion Criteria:

1. Adults \geq 18 years admitted to a participating hospital
2. Stage 1 Acute Kidney Injury as defined by KDIGO creatinine criteria:
 - a. 0.3 mg/dl increase in inpatient serum creatine over 48 hours OR
 - b. 50% relative increase in inpatient serum creatinine over 168 hours

Exclusion Criteria:

1. Admission to hospice service or comfort measures only order
2. Recipient of a solid organ transplant
3. Immediate dialytic indication determined by the following:
 - a. $K \geq 7$ meq/L
 - b. Acute ingestion of dialyzable toxin

- c. Refractory volume overload
- d. BUN > 150 mg/dL
- e. pH < 7.15 despite ventilatory support

4. Pre-existing CKD stage V or ESRD
5. Initial hospital creatinine > 4.0 mg/dl
6. Nephrology already consulted
7. Status post nephrectomy (partial or radical) during index admission

6 - Methods

6.1 Treatment - Device

6.1.1 Intended use for the device

Kidney Action Team Recommendations

Dedicated and trained Kidney Action Teams (KATs) will each consist of an advanced practitioner and a pharmacist and will be supervised by a nephrologist. KATs will be available 24 hours a day, 7 days a week, barring extenuating circumstances. The KAT will be notified, in real-time, of all randomized patients at their site who meet enrollment criteria via an automated electronic health record system. The KAT will be tasked with providing individualized recommendations for AKI workup and treatment based on best practices identified within several kidney domains. Recommendations will be created for each randomized patient, however, they will only be delivered to the primary care teams of those patients who have been randomized to the active intervention group. This strategy allows for both the blinding of the KAT as well as a comparison in the proportion of recommendations implemented between the control and intervention groups.

Recommendations for those in the intervention group will be made and delivered within one hour of AKI alert via a specialized note (Appendix 1) that is entered into the patient's chart and flagged for cosigning by the covering primary physician (i.e., the person signed on to EPIC as the patient's covering provider for that shift).

We have designed the recommendations to be limited to specific domains of AKI diagnosis and treatment in order to minimize the variability in recommendations across members of the Kidney Action Teams and to allow for timely recommendations to be made. These domains include potassium management, acid/base management, fluid management, drug redosing and cessation, and diagnostic work-up. We have also included a set of universal recommendations that will be delivered to all patients randomized to the intervention group, as we feel these to be a necessary component of a standard work-up for any AKI patient.

Universal AKI recommendations will be recommended if not yet performed in the 48 hours prior to randomization and include:

- Obtaining a urinalysis
- Obtaining a urine sodium, potassium, chloride, creatinine measurement
- Obtaining a post-void residual measurement or renal ultrasound to rule out obstruction
- Avoiding new nephrotoxic exposures
- Measuring serum creatinine at least every 24 hours during the inpatient stay
- Strict measurement of fluid input and output

Recommendations in the other domains will be personalized and may include the following:

Potential Recommendations for Potassium Management

- No recommendation
- Administer loop diuretic:
 - Furosemide 40mg IV x 1 dose
 - Furosemide 60mg IV x 1 dose
 - Furosemide 80mg IV x 1 dose
 - Furosemide 120mg IV x 1 dose
 - Furosemide 160mg IV x 1 dose
 - Administer metolazone 30 minutes prior to loop diuretic
- Other (specify)Low (2g) potassium diet
- Potassium binder (such as sodium polystyrene sulfate, patiromer, or sodium zirconium cyclosilicate)
- Lactated Ringer Bolus of 500ml
- Recheck potassium within 6 hours
- Recheck potassium within 2 hours
- Calcium Gluconate 9meq IV
- Insulin 5 units IV, with or without 50% dextrose
- Insulin 10 units IV, with or without 50% dextrose (1 amp IV)
- Nephrology Consult
- Telemetry Monitoring
- Other (specify)

Potential Recommendations for Acid/Base Management

- No recommendation
- Order ABG or VBG
- Check toxic alcohols
- Check lactate, beta-hydroxybutyrate
- Give 1L of isotonic sodium bicarbonate
- Start oral sodium bicarbonate (specify dose)
- Other (specify)

Potential Recommendations for Diagnostic Testing

- No recommendation
- Order urinalysis

- Order CK, Haptoglobin and LDH
- Consider renal consult
- Other (specify)

Potential Recommendations for Fluid Management

- No recommendation
- 1L Ringer's lactate bolus
- Albumin 25g x 1
- Albumin 50g x 1
- Caution with IV fluids if concern for respiratory compromise
- Check orthostatic vitals
- Re-assess volume status prior to further volume resuscitation
- Avoid IV fluids
- Obtain chest x-ray
- Obtain transthoracic echocardiogram
- Other (specify)

Potential recommendations for medication management:

- No medications to stop or dose adjust
- Stop NSAID
- Stop ACEi/ARB/mineralocorticoid antagonist/Renin Inhibitor
- Stop Proton Pump Inhibitor
- Stop other nephrotoxic medication (specify)
- Adjust the dose of this medication (specify)

Monitor the level of this medication (specify)Recommendations will only be made once for each patient (within one hour of AKI onset) and with no follow-up on results from these recommendations. We will clearly communicate this with all exposed physicians during our educational outreach. This ensures no post-randomization unblinding and will also increase generalizability by decreasing the burden on the Kidney Action Teams.

6.1.2 Device administration and schedule

The Kidney Action Team will provide personalized recommendations within 1 hour of the AKI alert being generated. This will be the sole interaction between the KAT and the study patient. No follow-up of recommendations will be performed.

6.1.3 Method of Assignment/Randomization

Randomization will be performed within REDCap using a computer-generated randomization table which will use permuted blocks (of 4, 6 and 8 individuals). Randomization will be stratified by study hospital.

The Kidney Action Team will create recommendations for all patients that meet eligibility criteria, regardless of randomization status, which will preserve their blinding.

(Recommendations will only be delivered to patients in the intervention group). Providers and patients will not be blinded. Study investigators and analysts will be blinded to randomization status.

6.1.4 Concomitant therapy

There are no restrictions on concomitant therapy in this trial.

6.2 Assessments

6.2.1 Safety/Pregnancy-related policy

Pregnant women and those who are of child-bearing age are not excluded from this study.

6.3 Study Procedures

6.3.1 Informed Consent

Due to the nature of the study, it is not feasible to consent subjects, as it would severely contaminate the exposure of interest. For example, a control subject who was sought out for consent might indicate to his/her provider that they were enrolled into the study and would reveal their AKI diagnosis. Further, it would be infeasible to consent patients in a timely manner (at the onset of AKI) that is needed for quick delivery of recommendations to the primary care team. To avoid these issues, we could obtain informed consent from every patient on admission to the hospital. However, given the incidence of AKI is approximately 15% of admissions, this would be impractical as well as unnecessary for the vast majority of patients, exposing roughly 85% of patients never deemed eligible for the trial to the risks of loss of confidentiality present in all research with human subjects. Given that the proposed research presents no more than minimal risk to subjects and that no procedures are being performed that require consent outside of the research paradigm, we request a waiver of informed consent for this study. Waiver of consent and HIPAA authorization from the BRANY IRB for all sites, including JHU and YNHH hospitals under their own potential IRB.

6.3.2 Screening

Screening of potential participants will be completed by an electronic AKI "sniffer" algorithm, already in place at the study hospitals. The algorithm will flag patients with AKI as defined in the inclusion criteria, and evaluate whether inclusion / exclusion criteria are met. The patient information will then be passed, in real time, to the Kidney Action Team who will assess eligibility for enrollment into this trial. The KAT will be able to complete a brief screening assessment prior to their formal evaluation to ensure that the patient is truly eligible as well.

6.3.3 Recruitment, Enrollment and Retention

As this study will be conducted under a waiver of informed consent, recruitment is automatic. We do note that the study hospitals have an "opt out" option for research that uses the electronic health record. These patients will not be enrolled in this study.

Patients will be followed electronically throughout their hospitalization. There are no formal study visits.

6.3.4 On Study Visits

There are no formal study visits.

6.3.5 End of Study and Follow-up

Follow-up will conclude at the time of discharge from the hospitalization in which the patient was randomized.

6.4 Statistical Method

6.4.1 Statistical Design

We will compare rates of the primary outcome of progression of AKI, dialysis and death using the Cochrane-Mantel-Haenszel chi-square test, accounting for stratification by hospital. We will average proportion of recommendations followed within 24 hours between the intervention and control group using the Van Elteren test to account for stratification by hospital.

6.4.2 Sample Size Considerations

We determined the overall sample size of this study based on the clinical composite outcome of progression of AKI, Dialysis, and Death. The baseline rate of this outcome is 21% based upon our preliminary data, and we felt that a relative 20% improvement (to 16.8%) would represent a clinically meaningful difference. In order to have 90% power to detect such a difference (or greater) at an alpha of 0.05, we would need to enroll 1,824 patients in each group, for a total of 3,648 in the study. Given concerns about contamination across the study arms (see III.L.9), we have increased this recruitment target by approximately 10% to a total of 4000 individuals. Table 2 shows a breakdown of recruitment by study site. Given the fact that this trial will operate under a waiver of informed consent, and our prior track record in this space, we expect full accrual across both sites within 3 years. Enrollment of 4000 individuals will also allow us to detect a difference in the rate of adherence to recommendations of 10% of one standard deviation at an alpha of 0.05, which is ample power to determine if the provision of these recommendations change provider behavior.

6.4.3 Planned Analyses

6.4.3.1 Primary Analyses

The primary analysis will compare the proportion of patients experiencing the primary outcome (progression of AKI, Dialysis, or Death) at 14 days after randomization. We will compare the difference using the Cochrane-Mantel_Haenszel chi-square test, accounting for stratification by study hospital.

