6.4.3.2 Analysis of Subject Characteristics

We will compare the baseline characteristics of subjects in the two study groups using chi-square tests (for categorical variables) and Wilcoxon Rank Sum tests (for continuous variables).

7 - Trial Administration

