7.5 Data Collection

- All participant data relating to the study will be recorded on printed or electronic CRF unless transmitted to the investigators electronically (e.g., laboratory data). The investigators are responsible for verifying that data entries are accurate and correct by physically or electronically signing the CRF.

Data will be obtained from the electronic health record via Yale's Joint Data Analytics Team (JDAT) as raw flat files from Clarity, the relational database from Epic. These files will then be transferred to our server via secure FTP. A deidentified dataset will be constructed by the study team using the Safe Harbor method of the HIPAA Privacy Rule, namely the removal of all 18 HIPAA identifiers.

Non PHI elements of this data pull will include the following (looking back a minimum of 10 years):

- Full patient medical history
- All available clinical care information during index encounter
- All available information from follow-up encounters following index hospitalization
- Provider type/class and location of treatment for all follow-up encounters following index hospitalization
- Patient coverage status
- The investigator must permit study-related monitoring, audits, IRB/IEC review, and regulatory agency inspections and provide direct access to source data documents.

- The investigators are responsible for the data management of this study including quality checking of the data.
- Records and documents, including signed ICFs, pertaining to the conduct of this study must be retained by the investigator for five years after study completion unless local regulations or institutional policies require a longer retention period.

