7.9 Study Monitoring

The study will be monitored by the internal team as well as a dedicated external Data and Safety Monitoring Board.

The DSMB will meet at least twice a year to review data and will have a formal meeting to assess the interim analysis results.

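### The primary hospital-stratified CMH test is valid but uses no pre-randomisation patient data, so the plan forgoes a modest gain in precision that would need no extra patients

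*Combined protocol and SAP*

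**What the plan says.** Sections 6.4.1 and 6.4.3.1 both give the Cochran-Mantel-Haenszel (CMH) test, stratified by hospital, as the analysis of the primary composite: "using the Cochrane-Mantel-Haenszel chi-square test, accounting for stratification by hospital" in the first and "We will compare the difference using the Cochrane-Mantel_Haenszel chi-square test, accounting for stratification by study hospital" in the second. Under section 6.1.3, hospital is the only stratification factor in the randomisation.

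The one stated use of baseline data is in section 6.4.3.2: "We will compare the baseline characteristics of subjects in the two study groups using chi-square tests" for categorical variables, with Wilcoxon tests for continuous ones. No adjusted primary, sensitivity or supportive analysis is described.

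The data for one are largely in hand. Section 7.5 lists medical history, with a look-back of at least ten years, and "All available clinical care information during index encounter". At screening (section 6.3.2), "The algorithm will flag patients with AKI as defined in the inclusion criteria, and evaluate whether inclusion / exclusion criteria are met". The criteria in section 5.3.2 rest on creatinine, potassium, BUN and CKD stage; one example is "Initial hospital creatinine > 4.0 mg/dl".

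**The concern.** In a randomised trial, adjusting for baseline variables that predict the outcome removes outcome variance that treatment does not explain. The interval narrows and power rises with no added patients. Here the plan would extract likely predictors of AKI progression, dialysis and death, and then use them only to test for imbalance between arms, which adds nothing to the precision of the treatment comparison.

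The benefit depends on how prognostic the variables are and is nil if they are not. Adjustment also does not correct dilution of the effect by contamination, which is the sponsor's stated reason for raising the target from 3,648 to 4,000.

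A separate reporting gap sits in the same place. Section 6.4.3.1 speaks of comparing a difference in proportions but names no estimator and no confidence interval. That costs no precision, and the same change would close it.

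**Working it through.** **Inputs from the plan (section 6.4.2).** Control rate 21%, intervention rate 16.8% (difference 0.042), 90% power, alpha 0.05; "we would need to enroll 1,824 patients in each group", raised to 4,000 in total, taken as 2,000 per arm. Sidedness is not stated; two-sided is used because it reproduces the plan's figure and one-sided does not (1,487).

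**Reproducing the plan's figure.** With pooled rate 0.189:

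- Null variance term: 2 × 0.189 × 0.811 = 0.306558
- Alternative variance term: 0.21 × 0.79 + 0.168 × 0.832 = 0.305676
- n per group = (1.960 × √0.306558 + 1.2816 × √0.305676)² / 0.042² = 1,823.96, rounded up to **1,824**, an exact match.

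**Power of the planned test at 2,000 per arm.** Φ[(0.042 × √2000 − 1.960 × √0.306558) / √0.305676] = Φ[(1.878 − 1.085) / 0.553] = **92.4%**.

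**Effect of adjustment.** If the covariates explain a share R2 of the outcome variance, the variance of the estimate is multiplied by (1 − R2). Then effective N = 4000 / (1 − R2), and the half-width is 1.96 × √[0.305676 / (2000 / (1 − R2))]. The documents give no R2, so a range is assumed.

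| Assumed R2 | Effective N | Power (formula) | 95% CI half-width (points) |
|---|---|---|---|
| 0% | 4,000 | 92.4% | 2.42 |
| 2% | 4,082 | 92.9% | 2.40 |
| 4% | 4,167 | 93.4% | 2.37 |
| 8% | 4,348 | 94.3% | 2.32 |
| 13% | 4,598 | 95.3% | 2.26 |

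**Simulation of the actual proposal.** The formula ignores the cost of fitting weak covariates and handling missing values, so the full model was simulated.

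- 10,000 trials per scenario, each with 4,000 patients in seven hospitals; hospital shares and effects were assumed, and arms were balanced within hospital.
- Seven independent normal covariates, four prognostic and three pure noise, with 10% of each missing at random, mean-imputed blind to arm, plus a missingness indicator. This gives a 22-parameter logistic model.
- The standardised risk difference, with influence-function standard errors and a degrees-of-freedom correction, was compared with stratified CMH on the same data. Null runs used 18.9% in both arms.

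| R2 | CMH power | Adjusted power | Paired gain (points) | Adjusted half-width (points) |
|---|---|---|---|---|
| 0% | 92.8% | 92.9% | 0.05 | 2.42 |
| 1.9% | 92.3% | 92.5% | 0.25 | 2.40 |
| 3.7% | 92.1% | 92.6% | 0.53 | 2.38 |
| 7.9% | 92.5% | 94.2% | 1.72 | 2.33 |
| 13.0% | 92.6% | 95.2% | 2.56 | 2.28 |

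The Monte Carlo standard error of the gains is 0.1 to 0.2 points. Type I error was 5.0 to 5.6% for the adjusted test (mean 5.2%) and 4.9 to 5.2% for CMH (mean 5.0%).

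A separate simulation of the same seven-covariate model gave gains of about 0.6, 1.2 and 2.5 points at R2 of about 4, 8 and 13%, and a similar gain of 1.4 points with correlated covariates. Its null rejection rates were 5.0 to 5.4% adjusted and 4.7 to 5.5% for CMH, within simulation error.

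**If the effect is smaller.** Suppose it is diluted to a 16% relative reduction (an assumption), so that the intervention rate is 0.21 × 0.84 = 17.64%. Power of the planned test is then 76.8%. With adjustment it is 78.5, 80.1 and 82.3% at R2 of 4, 8 and 13%.

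**The case against.** The strongest reply is that nothing is broken. The test is valid, the sample size reproduces, and the 90% target is met without adjustment. A simple stratified test is a defensible choice, and replacing the primary analysis of a protocol already at version 4 (May 2024), with an interim analysis planned, invites questions of credibility.

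R2 is also unknown. Eligibility narrows the range of creatinine, BUN and potassium, so the low end is plausible, and there the gain is close to nothing. Part of the low-end gain may not be efficiency at all: raising alpha from 0.050 to 0.052, the simulated average excess, lifts formula power from 92.43% to 92.67%. That 0.24 points is about the whole simulated gain at R2 of 2% and nearly half of it at 4%.

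Much of this stands. The point is about efficiency, and a gain at R2 of 2% or less should be counted as nil. The excess type I error is small and did not stand out from simulation error in the separate simulation, but it is a reason to keep the covariate list short. The excess does not account for gains of 1.7 to 2.6 points at R2 of 8 to 13%. The timing objection is met by making the change only while blind, with CMH otherwise staying primary.

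The data objection also stands in part: section 7.5 describes extraction only through Yale's data team, so availability at the two Johns Hopkins hospitals has to be confirmed.

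**Conclusion.** The concern holds as a missed efficiency. The planned primary test is sound and adequately powered on the plan's own assumptions, but it leaves unused the baseline information that the trial intends to extract. The cost is negligible if the covariates explain 2% or less of the outcome variance, about half a power point at 4%, and about 2 to 3 power points at 8 to 13%. At 8%, 4,000 patients would act like 4,348, a gain of 348 that is close to the 352 patients (4,000 − 3,648) added for contamination. Precision is worth more if the true effect is smaller than planned.

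These figures rest on an assumed R2, on assumed hospital sizes and effects, and in the main simulation on independent covariates and data missing at random. The change is worth making because it is cheap, but the trial does not depend on it.

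**What to change.** While blind, and before any interim or final comparison by arm, amend the plan as follows.

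- **Primary estimate.** The marginal risk difference with a 95% confidence interval, standardised from a logistic model with treatment, hospital and a short fixed list of covariates. This stays on the scale of the sample-size assumption and supplies the missing estimator and interval.
- **Covariates.** Age, reference creatinine, creatinine at the alert, potassium, BUN, ICU versus ward, and prior CKD, each the last value before randomisation. The restriction matters because the index-encounter extract also contains later data.
- **Inference.** Robust (influence-function) standard errors with a degrees-of-freedom correction.
- **Missing covariates.** Impute blind to arm and add a missingness indicator.
- **Interim.** Section 7.9 says the DSMB "will have a formal meeting to assess the interim analysis results". Use the same method there and at the final analysis.
- **Supportive analysis.** Keep the hospital-stratified CMH test.
- **Fallback.** If those setting the plan have already seen a comparison by arm, keep CMH primary and report the adjusted risk difference and interval as supportive.

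The cost is SAP text, a little code, coordination with the DSMB, and confirmation that these variables are extracted at the two Johns Hopkins hospitals. It needs no added patients and, once that is confirmed, no data beyond the planned extraction.

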6.4.3.2 Analysis of Subject Characteristics

We will compare the baseline characteristics of subjects in the two study groups using chi-square tests (for categorical variables) and Wilcoxon Rank Sum tests (for continuous variables).

7 - Trial Administration

7.1 Ethical Considerations: Informed Consent/Accent and HIPAA Authorization

The study will be conducted under a waiver of informed consent.

Due to the nature of the study, it is not feasible to consent subjects, as it would severely contaminate the exposure of interest. For example, a control subject who was sought out for consent might indicate to his/her provider that they were enrolled into the study and may subsequently affect provider behavior. Further, it would be infeasible to consent patients in a timely manner, at the onset of AKI, that is required for rapid delivery of recommendations to the primary care team. To avoid these issues, we could obtain informed consent from every patient on admission to the hospital. However, given the incidence of AKI is approximately 15% of admissions, this would be impractical as well as unnecessary for the vast majority of patients, exposing roughly 85% of patients never deemed eligible for the trial to the risks of loss of confidentiality present in all research with human subjects. Given that the proposed research presents no more than minimal risk to subjects and that no procedures are being performed that require consent outside of the research paradigm, we request a waiver of informed consent from the IRB.

Subjects will not be informed of their participation in the trial at a later date. Informing patients to the presence of AKI, which may be unfamiliar to most, may engender significant stress without offering any tangible benefit or guideline-based follow-up or intervention to pursue. Patients may also incorrectly assume that AKI is an iatrogenic condition caused by poor medical care, or that they were not receiving the full extent of medical care available in the absence of the recommendations when assigned to the control group. However, our study is simply synthesizing already available data from the electronic medical record and recommending a plan of care that is already available for physicians to utilize. We will, however, update all clinicians with the results after trial completion. While no data will be linked to any specific provider, we will be able to relay broader generalizations (e.g. personalized recommendations decrease the use of certain nephrotoxins).

